A Multi-center Clinical Study on the Efficacy and Safety of Kuntai Capsule Alone and in Combination With Hormones in the Treatment of Early-onset Hypoovarian Function

NCT05021094

Date: August 4, 2021

Research Proposal Summary

| Scheme number | HYKT18017S |
|------------------------|---|
| Scheme name | A Multi-center Clinical Study on the Efficacy and Safety of Kuntai Capsule Alone and in |
| | Combination With Hormones in the Treatment of Early-onset Hypoovarian Function |
| Version number/date | Version 2.1 , June 18 , 2021 |
| sponsor | Shanghai Haitian Pharmaceutical Technology Development Co., Ltd. |
| Clinical trial staging | Post-marketing clinical re-evaluation |
| test drug | Heyan Kuntai Capsules [®] (Z20000083), each0.5g, was produced by Guiyang Xintian Pharmaceutical Co., Ltd. |
| Indications | POI (including subclinical stage) |
| Test purposes | To evaluate [®] the efficacy and safety of Heyan Kuntai Capsules alone or in combination with hormone therapy in patients with POI (including subclinical stage) in improving ovarian function . |
| Research design | Prospective, multicenter, randomized, controlled clinical trial design |
| total number | It is planned to complete 120 cases (considering the 20% dropout rate, at least 150 cases need to be |
| of cases | enrolled) |
| number of research | 6_ |

| centers | |
|--------------|---|
| Study period | 24 months |
| research | Diagnostic criteria : |
| object | The diagnostic criteria for premature ovarian insufficiency (POI) refer to the "2017 Chinese |
| | Expert Consensus on Clinical Diagnosis and Treatment of Premature Ovarian Insufficiency" and |
| | "2016 Expert Consensus on Hormone Supplementation Therapy for Premature Ovarian |
| | Insufficiency"; including: (1) Age <40 years old; (2) oligomenorrhea or amenorrhea for at least 4 |
| | months; (3) at least 2 times serum basal follicle-stimulating hormone (FSH) > 25 IU/L (interval > 4 |
| | weeks). Subclinical POI: FSH level is 15~25 IU/L, which is a high-risk group. |
| | The diagnostic criteria for premature ovarian failure (POF) refer to the "2017 Chinese Expert |
| | Consensus on Clinical Diagnosis and Treatment of Premature Ovarian Insufficiency", which refers |
| | to amenorrhea, FSH>40IU/L, and decreased estrogen levels before the age of 40, accompanied by |
| | varying degrees of perimenopause Stage symptoms are the terminal stage of POI. |
| | standard constrain: |
| | 1. 18 years old ≤ age < 40 years old; |

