| | 2. At least two (>4 weeks interval) basal FSH≥15IU/L, with or without oligomenorrhea or |
| | menopause. |
| | 3. Informed consent, voluntary experiment. |
| | Exclusion criteria: |
| | 1. pregnant and lactating patients; |
| | 2. Patients with endometriosis , adenomyosis , endometrial lesions (submucosal fibroids , |
| | endometrial polyps, etc.), uterine fibroids >4cm or hysterectomy; |
| | 3. Patients with known or suspected history of breast cancer and estrogen-dependent |
| | malignancies; |
| | 4. a personal history of venous thromboembolism (VTE) or with a high risk of VTE (including |
| | body mass index > 30 kg/m ² , smoking, family history of thrombophilia); |
| | 5. Porphyria patients; |
| | 6. Patients with serious primary diseases such as cardiovascular, liver, kidney, hematopoietic |
| | system or mental illness; |

- 7. Patients who are participating in other clinical trials or have participated in other clinical trials within the past three months;
- 8. Patients with suspected or real history of alcohol and drug abuse;
- 9. Known allergy to the investigational drug or its components;
- 10. Other patients deemed unsuitable for participation in this trial by the investigator.

Note: Patients who were receiving hormone replacement therapy at the time of recruitment were required to take at least a 3 -month suspension of medication to participate in this trial.

Trial grouping

and medication

1 POI patient

According to the random sequence generated by computer, eligible patients were randomly assigned to Kuntai group, control group and combination group according to 1:1:1.

- (A) Kuntai group (30 cases): Oral Kuntai capsules, 4 capsules at a time, 3 times a day, 28 days as a course of treatment, taking medicine for 3 courses;
- (B) Control group (30 cases): the sequential regimen of estrogen and progesterone was used, and the drug was estradiol tablets/estradiol dydrogesterone tablets (fenmetone), and red tablets (estradiol, 2 mg/d), and gray tablets (estradiol, 2 mg/d, dydrogesterone, 10 mg/d) were taken for the next 14 days, 28 days as a course of treatment, and three courses of medication were taken.
- (C) Combination group (30 cases): On the basis of hormone therapy, Kuntai Capsules were added, and the dose was the same as that of Kuntai group and hormone group for 3 months.

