- 2. Patients with POI in subclinical stage: self-control before and after experiment group (30 cases): Oral Kuntai capsules, 4 capsules at a time, 3 times a day, 28 days as a course of treatment, taking medicine for 3 courses of treatment.

Treatment and

follow-up

- 1. Course of treatment: 28 days as a course of treatment, taking medicine for 3 courses of treatment
- 2. Visit points: before treatment (stage V $_{0}$, screening period, days -35 $\rm to~0$), baseline period (day
- 0), after 3 months of treatment (stage V_1 , days 84 to 105), drug withdrawal 3 months later (V_2 stage, 168-210 days) and 6 months after drug withdrawal (V_3 stage, 252-315 days).

Specific inspection items include:

- 1. The patient 's hormone levels (basal FSH, LH, E₂) were detected in V₀, V₁, and V₂ stages;
- 2 Anti-Müllerian hormone (AMH) was detected in patients at V 0 and V 1 stages;
- 3 The patients underwent B-ultrasound at V 0 and V 1 stage to monitor the follicular development,

| | record the number of antral follicles (AFC), ovarian hemodynamic parameters (PSV, EDV, S/D, RI |
|----------------|---|
| | and PI); |
| | 4. Modified Kupperman score was performed in V $_{0}$, V $_{1}$ and V $_{2}$ stage; |
| | 5 Pregnancy was recorded at the V $_2$ outpatient follow-up for patients with reproductive needs; |
| | 6 patients at V $_{0}$ and V $_{1}$ to detect blood routine (RBC, WBC, PLT, HGB) , liver function (ALT, |
| | AST) and renal function (BUN, Cr), and recorded adverse events. |
| | |
| | Note: |
| | 1 Basal follicle-stimulating hormone (FSH) \geq 15IU/L at first visit in patient V0, and if other |
| | inclusion criteria are met, if the patient has a history of testing with a baseline FSH ≥ 15 IU/L in |
| | the past (interval> 4 weeks), he or she can be included in this study and drug therapy can be |
| | started; (Interval > 4 weeks) If the basic FSH \geq 15 IU/L has not been diagnosed, the patient is |
| | required to visit the hospital again after 4 weeks. If the basic FSH is still \geq 15 IU/L, they can be |
| | included in this study and drug therapy can be started. |
| | 2 For patients with regular menstrual periods, the basal FSH and antral follicle count (AFC) |
| | should be followed up on the 2nd to 4th day of the menstrual cycle. If the patient has menstrual |
| | cramps after the follow-up and has not exceeded the visit window, they are required to re-examine |
| | on the 2nd to 4th day of the menstrual cycle and record the examination data. |

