| study endpoint | Primary endpoint : FSH, modified Kupperman score |
| | Secondary endpoints : |
| | (1) FSH/LH, LH, E ₂ ; (2) Antral follicle count (AFC); (3) Anti- Müllerian hormone (AMH); (4) |
| | Proportion of patients with normal menstruation; (5) Ovarian hemodynamics parameters (PSV, |
| | EDV, S/D, RI and PI); (6) Clinical pregnancy rate (patients with reproductive needs). |
| security | 1 Blood routine (RBC, WBC, PLT, HGB), liver function (ALT, AST) and renal function (BUN, |
| indicators | Cr); |
| | 2 Patient adverse events were recorded. |

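### The clinical pregnancy rate cannot be split into unassisted and assisted conceptions, because the posted documents neither record nor restrict fertility treatment

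*Protocol*

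**What the plan says.** The purpose, in the Test purposes row of the Protocol's Research Proposal Summary, is to assess Kuntai alone or with hormones "in patients with POI (including subclinical stage) in improving ovarian function".

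Under study endpoint, FSH and the modified Kupperman score are primary. Pregnancy is the last of six secondary items, given only as "Clinical pregnancy rate (patients with reproductive needs"). What counts as a clinical pregnancy is not defined, and mode of conception is not mentioned.

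Under Treatment and follow-up, inspection item 5 is the only collection rule: "Pregnancy was recorded at the V $_2$ outpatient follow-up for patients with reproductive needs". V2 falls at days 168 to 210. The other inspection items cover hormones, AMH, ultrasound, the Kupperman score and safety tests with adverse events. None covers concomitant treatment.

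Two provisions come near the subject, and both act at entry only. The note after the exclusion criteria says: "Patients who were receiving hormone replacement therapy at the time of recruitment were required to take at least a 3 -month suspension of medication". Exclusion 10 leaves a discretion: "Other patients deemed unsuitable for participation in this trial by the investigator". None of the ten exclusions names ovulation induction, IVF or donor eggs.

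The SAP's single paragraph applies a chi-square test to counts and repeated-measures ANOVA to measurements over time. It has no rule for assisted conceptions or for hormone values drawn during pregnancy.

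**The concern.** The endpoint is confined to women who want to conceive, who are the women with a reason to seek fertility treatment. They are observed for some months after study treatment ends, and the posted text places no limit on what they do in that time.

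A donor-egg pregnancy says nothing about the woman's own ovaries. A pregnancy after stimulation or IVF with her own eggs mixes the effect of the fertility treatment with any effect of the study treatment. If neither the treatment nor the mode of conception is recorded, the rate cannot be separated afterwards, and it cannot cleanly inform a question about ovarian function.

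The regimens differ visibly and no blinding is described, so a decision to seek fertility treatment could depend on the arm. The subclinical group has no comparator to absorb the problem.

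A related gap is that FSH, LH and E2 are also scheduled at V2, and the documents do not say what happens to these values in a woman who is pregnant then.

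**Working it through.** **The plan's own figures.** Three randomised arms of 30 plus 30 subclinical cases give 3 × 30 + 30 = 120 completers. With 20% dropout, 120 / (1 − 0.20) = 150, as the Protocol states. This point does not affect that figure. The documents give no pregnancy rate, no uptake of fertility treatment and no number of women with reproductive needs, so all later inputs are assumptions, shown as ranges.

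**Time at risk.** Three 28-day courses end at about day 84. V2 at days 168 to 210 is therefore 84 to 126 days later.

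**Weight of one assisted pregnancy.** With m women with reproductive needs in an arm, each assisted pregnancy adds 1/m to its rate:
- m = 10: 1/10 = 10.0 percentage points
- m = 15: 1/15 = 6.7 points
- m = 30: 1/30 = 3.3 points

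**Share of counted pregnancies that are assisted.** Let q be the unassisted rate, s the uptake and r the success per treated woman. The observed rate is (1 − s)q + sr, and the assisted share is sr divided by that. With q = 5%:
- s = 10%, r = 10%: 0.010 / 0.055 = 18%
- s = 50%, r = 50%: 0.250 / 0.275 = 91%

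**Equal uptake.** If s and r are the same in two arms, the observed difference is (1 − s)(q₁ − q₂). At s = 10% to 50%, a true difference shrinks to 90% to 50% of its size. With no drug effect there is no bias. In simulations with q = 5%, 10% uptake in both arms and r of 30% or 50%, the uncorrected chi-square reached P<0.05 in 0.4% to 0.8% of trials at m = 10, 1.4% to 2.2% at m = 15 and 4.6% to 5.3% at m = 30.

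**Unequal uptake, no drug effect, q = 5%.**
- Uptake 30% against 10%, r = 30%: rates are 0.70 × 0.05 + 0.30 × 0.30 = 12.5% and 0.90 × 0.05 + 0.10 × 0.30 = 7.5%. Significant in 1.4%, 4.0% and 10.3% of simulated trials at m = 10, 15 and 30.
- Uptake 50% against 10%, r = 50%: rates are 0.50 × 0.05 + 0.50 × 0.50 = 27.5% and 0.90 × 0.05 + 0.10 × 0.50 = 9.5%. Significant in 11.9%, 23.8% and 44.1%.

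**How many are needed to change a test result.** Start from one unassisted pregnancy per arm and add assisted ones to one arm only. For m = 10 to 30, two give chi-square P of 0.264 to 0.301, three give 0.121 to 0.161, and five give 0.019 to 0.044. One or two visibly change the rates but do not produce significance.

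**Hormone values at V2.** Suppose, as an assumption, that one pregnant woman in an arm of 30 has an FSH of about 1 IU/L instead of 30 to 60. The arm mean falls by (30 − 1)/30 = 0.97 to (60 − 1)/30 = 1.97 IU/L, or about 3.3% of a mean of 30 or 60. No standard deviation is given against which to judge this.

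**The case against.** The strongest reply is that this argues from silence. The posted Protocol is headed as a summary, and a fuller protocol or CRF might capture fertility treatment. A reader might infer that the plan counts every pregnancy as a success, but the text does not say so; it leaves clinical pregnancy undefined. What stands is that the posted documents give no means of separating the conceptions.

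A reader might also infer that an assisted pregnancy is credited to the study drug. In the randomised arms it counts for whichever arm it occurs in, including the hormone control. Only in the subclinical group, where all women take Kuntai, does each such pregnancy follow the study drug by design.

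The more striking error rates need an uptake gap of 50% against 10% with 50% success, and no document supports those values. Nor do the documents show that donor-egg treatment is likely before V2. A cycle with the woman's own eggs still depends partly on her ovaries, and counting all pregnancies whatever treatment follows is a legitimate treatment-policy choice. That is why the all-pregnancies rate should stay in the report. It does not remove the need to know which pregnancies were unassisted.

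Finally, it is tempting to say that V2 hormone values in pregnant women will be analysed as ordinary basal values. The documents do not say this. They call for basal hormones and tie basal FSH to cycle days 2 to 4 only for women with regular periods, so handling in pregnancy is simply unstated. Dropping such values from the main contrast would select on a post-treatment outcome, could remove women who responded, and under conventional repeated-measures ANOVA could lose a woman's whole record.

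**Conclusion.** The point holds for a secondary endpoint. On the posted documents, the pregnancy rate cannot be divided into unassisted and assisted conceptions, so it is weak evidence about ovarian function. Equal uptake dilutes the randomised comparison and unequal uptake biases it, in a direction that cannot be known in advance. The subclinical group has no comparison to protect it.

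The size is 3.3 to 10 percentage points per assisted pregnancy, assuming 30 down to 10 women with reproductive needs per arm. The simulated error rates only illustrate the mechanism. The primary conclusions do not rest on the pregnancy rate. The link to V2 FSH is a gap in stated handling with a modest illustrative effect, and it does not show that a primary endpoint is compromised.

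**What to change.** - Define clinical pregnancy. Record mode of conception (spontaneous, stimulated, IVF with own eggs, donor egg) and any fertility treatment, with dates, from day 0 to the pregnancy assessment. Starting only at the end of treatment would miss the treatment period itself.
- Report all clinical pregnancies by group. Report unassisted conceptions separately as the measure relevant to ovarian function, keeping all women with reproductive needs in the denominator. Show uptake of fertility treatment by arm beside it, because a woman who conceives with assistance can no longer contribute an unassisted event, and unequal uptake would affect this measure too.
- Flag hormone values drawn during pregnancy at V2, and show the FSH, LH and E2 results with and without them as a sensitivity analysis. Do not exclude them from the main contrast.

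The cost is two CRF fields, a few sentences in the endpoint definition and SAP, and fewer events in the unassisted analysis. Patient care does not change. Mode of conception is hard to reconstruct reliably later, so it should be collected prospectively.

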A Multi-center Clinical Study on the Efficacy and Safety of Kuntai Capsule Alone and in Combination With Hormones in the Treatment of Early-onset Hypoovarian Function

NCT05021094

Date : August 4 , 2021

Statistical analysis

The case observation form completed by the test center was reviewed and returned by the project team of Shanghai Haitian Pharmaceutical Technology Development Co., Ltd., and the data was processed by a statistical analyst. The data in the case report form is entered in two copies, and the database is locked after verification and confirmation. SPSS26.0 software was used for statistical analysis. The full analysis set (FAS) and the per-protocol set (PPS) were used for effectiveness analysis, and the safety data set (SS) was used for safety analysis. Measurement data were expressed as mean \pm standard deviation ($\bar{x} \pm s$), multiple time points were compared by repeated measures analysis of variance, and pairwise comparisons were by Bonferroni test; enumeration data were expressed by the number of cases or percentages, and χ^2 was used.Test for statistical comparison.P<0.05 indicated that the difference was statistically significant.

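### The SAP gives no safety-specific analysis, and its general rules are weak at showing isolated lab abnormalities or sparse adverse events

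*SAP*

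**What the plan says.** The SAP is one paragraph under *Statistical analysis*. It assigns safety to a named set ("the safety data set (SS) was used for safety analysis") but neither defines that set nor gives it a method. Two rules for all data follow. Measurement data are shown as mean ± SD, and "multiple time points were compared by repeated measures analysis of variance, and pairwise comparisons were by Bonferroni test". For counts, "enumeration data were expressed by the number of cases or percentages", with chi-square for comparison. The only criterion is that "P<0.05 indicated that the difference was statistically significant".

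The protocol's row on safety indicators lists "Blood routine (RBC, WBC, PLT, HGB), liver function (ALT, AST) and renal function (BUN" and Cr, which makes eight labs, and adds that "Patient adverse events were recorded". Item 6 of the inspection list under *Treatment and follow-up* places the blood tests at V0 and V1, so each woman has one planned post-baseline value. POI patients are "randomly assigned to Kuntai group, control group and combination group according to 1:1:1", 30 per arm. A further 30 subclinical patients form a single self-controlled group.

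Neither document contains a shift table, a count of values outside reference limits, a patient listing, a confidence interval or a rule for sparse counts.

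**The concern.** Safety is half of the trial's stated purpose, yet the plan treats safety data exactly as it treats efficacy data. Liver, kidney or blood toxicity often appears as a large change in one or two people. A group mean of 30 dilutes such a change, and the same outlier inflates the SD, so a test on the mean becomes less likely to react as the abnormality becomes more extreme.

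Adverse events in groups of 30 will often give small expected cell counts, where Pearson chi-square is not dependable and power is low. Because P<0.05 is the only yardstick and no interval is planned, a report that followed the plan could contain nothing but non-significant safety results while the data still allowed an important excess. The conclusion at risk is the safety statement for Kuntai alone and in combination. The primary efficacy analysis is not affected.

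**Working it through.** **The plan's own figure.** 4 groups × 30 = 120 completers; 120 / (1 − 0.20) = 150 enrolled, as the protocol states. That is 150 / 4 = 37.5 per group at enrolment. No safety sample-size figure is given.

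**Inputs.** From the documents: n = 30 per group, labs at V0 and V1, alpha 0.05. Assumed, because the documents do not give them: two-sided testing; ALT at V0 with mean 20 and SD 8 U/L; V1 = 20 + 0.5 × (V0 − 20) + noise with SD 7; all event rates.

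**Labs: why the mean test fails.** With two time points, repeated-measures ANOVA within a group is the paired t-test (F = t²). Suppose k of n women have the same very large change and the rest have none. The mean change is D·k/n, and the variance is D²·(k/n)(1 − k/n)·n/(n − 1). This gives

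t = √[k(n − 1)/(n − k)],

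in which D cancels. For n = 30:
- k = 1: √(29/29) = 1.00
- k = 2: √(58/28) = 1.44
- k = 3: √(87/27) = 1.80
- k = 4: √(116/26) = 2.11

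The critical value on 29 df is 2.045. In this limit up to three women cannot produce P<0.05, however extreme their values.

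**Labs: simulation under the assumed ALT model** (20,000 runs per row, k of 30 women set to the stated V1 value). The between-arm test compares change with an unaffected arm.

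| V1 value | k | Mean change (U/L) | Paired test P<0.05 | Between-arm test P<0.05 |
|---|---|---|---|---|
| 120 | 1 | 3.3 | 0.5% | 1.8% |
| 120 | 2 | 6.7 | 1.9% | 4.9% |
| 120 | 3 | 10.0 | 13% | 19% |
| 120 | 4 | 13.3 | 52% | 51% |
| 200 | 1 | 6.0 | 0% | 0.1% |
| 200 | 2 | 12.0 | 0.03% | 0.7% |
| 200 | 3 | 18.0 | 4% | 12% |
| 200 | 4 | 24.0 | 64% | 66% |

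For one or two women, neither test rejects more often than its nominal 5%. A uniform rise of 5 U/L is found in 91% of paired tests and 65% of between-arm tests, so the mean test does work for broad shifts. A second model (SD 7, correlation 0.6) gave between-arm rejection of 0%, 0.3% and 7.6% for one, two and three women at 200, the same pattern.

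**Adverse events: sparse cells.** In two arms of 30 the expected event count per arm is half the total, so at least 10 events are needed for expected counts of 5. For 4/30 v 0/30 the expected count is 2. Pearson gives χ² = 4.29, P = 0.038; Fisher gives P = 0.11. The choice of test decides significance.

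**Adverse events: power.** Exact enumeration of uncorrected Pearson chi-square, assumed rates:

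| Rates | 30 v 30 | 37 v 37 |
|---|---|---|
| 3% v 10% | 17% | 23% |
| 5% v 15% | 26% | 33% |
| 5% v 20% | 45% | 54% |
| 10% v 30% | 50% | 59% |

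**What intervals would show.** Zero events in 30 leaves a true rate of up to 1 − 0.05^(1/30) = 9.5% (one-sided 95%). For 3/30 v 0/30 the difference is 10 points, Newcombe 95% CI −3.1 to 25.6. Pearson P = 0.076 would be called non-significant, although the data allow an excess of about 25 points.

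**The case against.** The strongest reply is that the SAP does not say how labs or adverse events will be analysed. It names neither in its rules, and the repeated-measures rule speaks of multiple time points, of which the labs have two. That is fair, and it sets the limit of this point: the rules reach safety data only because no other rule exists.

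A reader might also infer that the SAP hides toxicity, or that it treats a non-significant test as proof of safety. The documents support neither. Event counts are to be shown as cases or percentages, so they are described as well as tested. A marked lab value could surface as a recorded adverse event, although nothing requires it. The SD is shown too: in the assumed model one woman at 200 U/L turns about 20 ± 8 into about 26 ± 34, which an alert reader would notice. Nowhere does the SAP equate P>0.05 with safety; it leaves that reading open by offering no other criterion.

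Two further objections stand in part. Mean tests detect broader shifts, so there is no case for dropping them. Low power for adverse events is usual at this size and better tables will not raise it; if the safety set holds nearer 37 per group, power and bounds improve somewhat. That is an argument for intervals, which show the uncertainty that a bare P value conceals. It is no argument for leaving the plan as it is.

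**Conclusion.** The point holds as an omission with a measurable consequence. With no safety-specific analysis, the default rules are nearly blind to one or two severe lab changes in a group of 30, and they give unreliable, low-powered comparisons when adverse events are few. The algebraic result, that up to three identical extreme changes in 30 cannot reach P<0.05, depends on n and on the idealisation that the other women do not change. The simulated percentages depend on assumed ALT values, and the power figures on assumed event rates and two-sided testing. None of these comes from the documents. The risk is that non-significance could be misread as safety, not that the plan prescribes that reading. This is a cheap and worthwhile improvement that should be made.

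**What to change.** Add a short safety section to the SAP:

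- Define the safety set, so that denominators are fixed.
- Keep mean ± SD for the labs. Add, for each of the eight labs and each group, a V0-to-V1 shift table (low, normal, high) against the site's reference range, the number of women newly abnormal at V1, and a listing of those women.
- Report women with at least one adverse event per group as n (%) with exact 95% confidence intervals.
- Where expected counts fall below 5, use Fisher's exact test in place of chi-square. Fisher is conservative (power 24% for 5% v 20% at 30 per arm), which is a further reason not to lean on the P value.
- State that the safety conclusion rests on the estimates and intervals, not on P>0.05.
- Treat any rate pooled over the 90 planned Kuntai-exposed women as descriptive only, because it mixes randomised arms, a hormone co-treated arm and an uncontrolled subclinical group. Zero events in 90 would bound the rate at 1 − 0.05^(1/90) = 3.3%, one-sided.

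The cost is SAP wording, a few more tables from data already collected, and each site's reference ranges in the CRF. The intervals will be visibly wide, which is accurate for groups of this size.

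### The planned repeated-measures ANOVA names no baseline covariate; adjusting the three randomised arms for V0 would sharpen the pairwise comparisons on FSH and the Kupperman score at almost no cost

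*SAP*

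**What the plan says.** The Protocol's study endpoint entry reads "Primary endpoint : FSH, modified Kupperman score". Under Treatment and follow-up, the hormone levels including FSH "were detected in V₀, V₁, and V₂ stages", and the modified Kupperman score follows the same three visits. AMH, antral follicle count and ovarian haemodynamics are recorded at V0 and V1 only.

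Under Trial grouping and medication, POI patients are "randomly assigned to Kuntai group, control group and combination group according to 1:1:1", with 30 cases in each arm. The subclinical patients form a separate, non-randomised "self-control before and after experiment group (30 cases").

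The SAP's Statistical analysis section is a single paragraph. For continuous data it states that "multiple time points were compared by repeated measures analysis of variance, and pairwise comparisons were by Bonferroni test". It says that "SPSS26.0 software was used for statistical analysis" but names no procedure. It lists a full analysis set and a per-protocol set for efficacy and sets significance at P<0.05. It does not say:

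- whether V0 enters as a repeated level or as a covariate;
- whether the arms are compared through a group effect, a group-by-time effect or a contrast at one visit;
- whether the Bonferroni pairs are arms or time points.

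**The concern.** In a randomised comparison the pre-treatment value usually explains part of the variation in the follow-up value. An analysis that ignores V0, or uses it only as one more level of a repeated factor, gives up precision that is available at no cost. With 30 planned completers per arm, that loss falls on both primary endpoints.

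The loss depends on how the SAP is read:

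- **Contrast at one visit.** It is either a raw comparison at that visit or, if V0 is a time level, in effect a comparison of change from V0. Both are less precise than V0 adjustment.
- **Group main effect averaged over V0, V1 and V2.** Treatment cannot have acted at V0, so including it shrinks an effect that is equal at V1 and V2 to two thirds. For endpoints measured only at V0 and V1 it shrinks to one half.

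A secondary, conditional point concerns missing data. If the analysis is run with a complete-case procedure, such as SPSS GLM Repeated Measures without imputation, a patient who misses V2 also loses her observed V1 value. The Protocol allows for 20% dropout, so this could affect a material share of patients. The documents give no dropout mechanism, so no bias is claimed.

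**Working it through.** **The plan's own figure.** 4 groups × 30 = 120 completers, and 120/(1−0.20) = 150 to enrol, as stated. The documents give no basis for the 120, so there is no planned power to reproduce.

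**Inputs.** From the documents: 30 per arm, three randomised arms, visits V0, V1 and V2, significance level 0.05. Assumed: two-sided testing, a difference of d = 0.6 SD, equal SDs, a common correlation r between visits (0.3 to 0.8), and, where Bonferroni is applied, three arm pairs (0.05/3 = 0.0167).

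**Variance of a pairwise contrast at one visit**, in units of 2σ²/n:

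- raw visit value: 1
- change from V0: 2(1−r)
- V0-adjusted: 1−r²

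Adjusted over change is (1−r²)/[2(1−r)] = (1+r)/2. Adjusted over raw is 1−r². Dividing 30 by each ratio gives the unadjusted number per arm that matches 30 adjusted.

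| r | ratio vs change | equivalent n | ratio vs raw | equivalent n |
|---|---|---|---|---|
| 0.3 | 0.65 | 46 | 0.91 | 33 |
| 0.5 | 0.75 | 40 | 0.75 | 40 |
| 0.7 | 0.85 | 35 | 0.51 | 59 |
| 0.8 | 0.90 | 33 | 0.36 | 83 |

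**Power** from the noncentral t distribution. Effective sizes are d/√(2(1−r)) for change and d for raw (58 df), and d/√(1−r²) for adjusted (57 df). At r = 0.5 the adjusted size is 0.6/√0.75 = 0.69.

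| r | α=0.05: change / raw / adjusted | α=0.0167: change / raw / adjusted |
|---|---|---|
| 0.3 | 49 / 63 / 67% | 32 / 45 / 49% |
| 0.5 | 63 / 63 / 75% | 45 / 45 / 59% |
| 0.7 | 84 / 63 / 89% | 70 / 45 / 78% |
| 0.8 | 95 / 63 / 97% | 88 / 45 / 92% |

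At r = 0.5, other effect sizes give 33% against 42% adjusted (0.4 SD) and 93% against 98% adjusted (0.9 SD), at α = 0.05.

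**Group main effect including V0**, with the same effect at V1 and V2. Over three visits the effective size is (2/3)d/√((1+2r)/3), giving 55% power at r = 0.3 and 37% at r = 0.8. Over two visits (V0 and V1) it is (d/2)/√((1+r)/2), giving 29% falling to 23%.

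**Omnibus group-by-time test**, three arms, 4 and 174 df, effect in one arm only. The noncentrality is 30 × (sum of squared interaction effects)/(1−r). If the V2 effect is full or absent, the sum is (2/3)(2/3)(0.36) = 0.16 and the noncentrality is 4.8/(1−r). If the V2 effect is half, the sum is (2/3)(1/2)(0.36) = 0.12 and the noncentrality is 3.6/(1−r).

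| r | V2 effect full or absent | V2 effect half | adjusted pairwise at V1 |
|---|---|---|---|
| 0.3 | 52% | 40% | 67% |
| 0.5 | 68% | 54% | 75% |
| 0.7 | 90% | 79% | 89% |
| 0.8 | 98% | 94% | 97% |

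**Simulation check** (4,000 three-arm trials per setting, full V2 effect). Change / raw / adjusted / omnibus power was 49/63/66/53% at r = 0.3, 62/63/74/68% at 0.5, 84/62/89/90% at 0.7 and 95/63/96/98% at 0.8. Under the null at r = 0.5, rejection rates were 5.5, 4.6, 5.1 and 5.2%, so adjustment did not inflate the Type I error.

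**The case against.** The strongest reply is that the SAP does not define the comparator. It speaks of comparing time points, so any gain is measured against a reading supplied from outside. V0 is probably already one of those time points, and the group-by-time test then uses it. Against that test, with a full or absent V2 effect, there is no gain from r of about 0.7. That part stands as arithmetic. However, the omnibus test asks a different question and does not say which arms differ. The SAP itself plans pairwise comparisons, and with V0 as a level the pairwise contrast at a visit is a change-score contrast, which V0 adjustment still improves.

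Other points have some force:

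- **r is unknown.** The gains over change and over raw values are not both large at the same r. Entry on FSH of at least 15 IU/L may lower r for FSH; that reduces the gain over raw values and increases it over change scores.
- **Which FSH is V0?** The Protocol has a screening window, a separate day-0 baseline, historical qualifying values and possible re-examination. The value must be defined, but the planned ANOVA has the same need.
- **Unequal slopes.** Two arms receive hormones and one does not, so the slope on V0 could differ by arm and a pooled slope need not help every pair. With assumed slopes 0.8/0.1/0.1 the pooled slope is 0.33. For the two 0.1 arms, the V0-related variance rises from 2(0.1²) = 0.02 to 2(0.23²) = 0.11 in V0-variance units. This is an assumed extreme and does not bias the contrast.
- **Larger analysis set.** With about 37 per arm (150/4), power at r = 0.5 is 72% against 84%, so the gain remains.
- **Brevity.** The SAP is one paragraph, and the complete-case point depends on a procedure it does not name. That point is therefore only conditional.

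**Conclusion.** The concern holds as an efficiency point: the planned method is valid and no bias is alleged. For a pairwise contrast of randomised arms at a given visit, V0 adjustment cuts variance by 10 to 35% against change from V0, and by 9 to 64% against the raw visit value, for r between 0.3 and 0.8. At an assumed 0.6 SD and r = 0.5, this is 63% to 75% power at 0.05, or 45% to 59% at 0.0167.

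These figures rest on equal SDs, a common correlation and a common slope. They illustrate a range and do not predict this trial's power. The change is worth making because it costs little and serves both primary endpoints.

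**What to change.** Amend the SAP for the three randomised arms as follows:

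1. For FSH, the Kupperman score and other continuous endpoints measured at V0, V1 and V2, fit a mixed model (SPSS MIXED) to the V1 and V2 values. Include arm, visit, arm-by-visit and the V0 value as covariate, and all randomised patients with any post-baseline value.
2. For continuous endpoints measured only at V0 and V1, use ANCOVA of V1 on V0.
3. Keep Bonferroni and state that it covers the pairwise arm contrasts.
4. Name the primary visit in advance. V1, the end of treatment, is a reasonable option, but the documents do not dictate it.
5. Define V0 in one line, for example as the last value before treatment starts.
6. Keep V0 as a time level for the single-arm subclinical before-after cohort.

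The cost is SAP wording, the sponsor's decision on the primary visit and the line defining V0. Software, visits, data and sample size do not change. Results would be reported as adjusted differences.
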